8.2 Washout Period

Following the final dose of IMP in Treatment Period 1, in the morning of Visit 5 (Day 21), patients will discontinue treatment with IMP for at least 7 days prior to Visit 6 (Day 31). This represents the washout period between the 2 treatment periods of this crossover trial.

8.3 Concomitant Therapy

From Screening (Visit 1) forward, any new treatments taken or any change to ongoing medications during the patient's participation in the trial will be recorded on the appropriate electronic case report form (eCRF) page by the investigator or designee. Similarly, any ongoing physiotherapy as part of the management of spasticity at the time of enrollment will be documented on a separate eCRF page as well as any changes in physiotherapy regimen that occur in the course of the study (e.g., discharge from physiotherapy).

For details about the potential for interactions from initiating IMP with prior medications, refer to the guidance for the investigator and potential drug interactions within the IB¹⁵.

8.3.1 Concomitant Optimized Multiple Sclerosis Antispasticity Medications

As nabiximols is being investigated as therapy in patients with spasticity due to MS, all patients must currently be taking at least 1 optimized oral MS antispasticity medication. Optimized oral MS antispasticity medications will include at least baclofen, tizanidine,

and/or dantrolene (monotherapy or combination therapy). Their MS antispasticity medication must have been stable for at least 30 days prior to Screening (Visit 1) and the medication is expected to remain stable throughout the duration of the trial. However, despite this optimization, eligible patients do not have adequate relief of their spasticity, including muscle spasms. Optimization of antispasticity medications is defined as having reached the most efficacious and best tolerated dose according to the relevant local prescribing information. The patient must be willing to maintain the same antispasticity therapy for the duration of the trial.

Benzodiazepines use is allowed if doses and dosing regimen have been stable for at least 30 days prior to Visit 1.

If the patient is currently receiving an approved MS disease-modifying therapy or dalfampridine or fampridine, it must be at a stable dose for at least 3 months prior to Visit 1 and is expected to remain stable for the duration of the trial.

8.4 Prohibited Therapy During Trial Period

The following medications are prohibited for the duration of the trial:

- Cannabis use for medical or recreational purposes or any cannabinoid-based medication within 30 days of Visit 1 and for the duration of the trial
- Botulinum toxin injection for the relief of spasticity within 6 months of Visit 1 and for the duration of the trial
- Antipsychotic medication
- Any benzodiazepines use on an as-needed (PRN) basis
- Drugs that are solely metabolized by UGT1A9 and UGT2B7 (see [Appendix 4](#)).
- Strong CYP3A4 inducers (e.g., rifampicin, carbamazepine, phenytoin, phenobarbital, St John's Wort)

Any patients taking these medications after Visit 1 may be considered for withdrawal from IMP.

8.5 Compliance in Investigational Medicinal Product Administration

The patient will record the number of sprays administered on each treatment day in the electronic diary.

Patients should return all IMP (used and unused) at each of Visits 4, 5, 8, and 9. The electronic diary-reported dosing information and any discrepancies discussed with the

patient at the time of the visit will be checked and documented accordingly within the patient's source documents.

Records of IMP accountability will be maintained according to [Section 5.3.4](#).

8.6 Access to Blinded Treatment Assignment

The identity of IMP assigned to patients will be held by the IRT. The principal investigator (PI) at each site, or his or her designee, is responsible for ensuring that information on how to access the IRT for an individual patient is available to the relevant staff in case of an emergency and unblinding is required. A patient's treatment assignment should only be unblinded when knowledge of the treatment is essential to make a decision on the medical management of the patient. Unblinding for any other reason will be considered a protocol deviation.

The investigator is encouraged to contact GW to discuss the rationale for unblinding prior to doing so. However, to prevent delays to the investigator or medical personnel responding to a potentially emergent situation, unblinding of IMP will not be dependent on the investigator receiving approval from GW (i.e., the investigator will be able to obtain the code break information independent of contacting GW).

If the investigator does unblind, he or she must contact GW within 1 working day of the event and must document the time, date, and reason(s) for unblinding in the patient's medical notes and on the eCRF.

9 TRIAL PROCEDURES

A list of the required trial procedures is provided in the subsections that follow; refer also to the schedule of assessments ([Appendix 1](#)). Assessments or tests that are not done and examinations that are not conducted must be reported as such on the eCRF.

Additional procedures to screen for the presence of or immunity against infectious diseases (such as body temperature, sampling of nasal or pharyngeal mucosa or serology) may be conducted at screening, at the beginning of each visit or as needed, according to local guidance and policy.

The location of the source data for the following procedures will be documented, per site, in a signed source data verification plan; for further details, see [Section 16.2](#).

In cases where patients are not able to attend study visits due to the presence of an infectious disease or other transmissible condition, the investigator will discuss with the Sponsor potential mitigation approaches (including but not limited to extending the visit window, conducting evaluations via video link or phone call, allowing for safety procedures to be conducted at the patient's home or local facility, or implementing potential mitigation approaches for IMP dispensing, secure delivery, and collection). The rationale (e.g., the specific limitation imposed by the infectious disease that led to the inability to perform the protocol-specified assessment) and outcome of the discussion will be documented in the medical record.

9.1 Trial Procedures by Visit

Patients will be invited to take part in the trial and will be issued with the patient information and informed consent. Following adequate time to discuss the trial with the investigator, nurse, relatives, or caregiver, as wished, patients who provide written informed consent will be screened for entry into the trial.

9.1.1 Screening (Visit 1 [Days -28 to -1])

Informed consent (see [Section 9.2.1](#)) must be obtained from the patient prior to beginning any trial-related procedures.

The following assessments/procedures will be performed:

- Eligibility check ([Section 6](#))
- Demographics ([Section 9.2.3](#))
- Previous cannabis use ([Section 9.2.4](#))

- Medical history ([Section 9.2.5](#))
- Electronic diary training ([Section 9.2.14.1](#))
- Concomitant medications review ([Section 9.2.6](#))
- AE review ([Section 9.2.17](#))
- Physical examination (including height measurement; [Section 9.2.7](#))
- Oral mucosa examination ([Section 9.2.8](#))
- Body weight measurement ([Section 9.2.9](#))
- Vital signs measurement ([Section 9.2.10](#))
- 12-lead ECG ([Section 9.2.11](#))
- Clinical laboratory blood sampling (hematology and biochemistry) ([Section 9.2.12](#))
- Dipstick urinalysis ([Section 9.2.12](#))
- Urine drug screen (including THC) ([Section 9.2.12](#))
- Serum pregnancy test (if appropriate) ([Sections 9.2.2 and 9.2.12](#))
- Blood THC test ([Section 9.2.12](#))
- MAS assessment ([Section 9.2.15.1](#))
- C-SSRS assessment ([Section 9.2.15.3](#))

The investigator should review the laboratory results as soon as these become available. If the results show that a patient is ineligible, the patient will fail screening.

Following Visit 1, there will be no changes in the dose of the patient's current oral MS antispasticity medications.

Patients who satisfy all of the inclusion criteria and none of the exclusion criteria specified in [Section 6](#) will enter a baseline period of at least 7 days prior to Visit 2, during which they will be required to take their optimized oral MS antispasticity medication (that must include at least 1 of baclofen, tizanidine, or dantrolene) and complete an electronic daily diary to record their 11-point NRS spasticity score, spasm count, and use of antispasticity medications once daily, around the same time each day, preferably in the evening before retiring to sleep.

9.1.1.1 Screening Failures

Screen failures are defined as participants who consent to participate in the clinical trial but are not subsequently randomly assigned to trial intervention. A minimal set of screen failure information is required to ensure transparent reporting of individuals who failed screening in order to meet the Consolidated Standards of Reporting Trials publishing

requirements and to respond to queries from regulatory authorities. The minimal information includes demography, screen failure details, eligibility criteria, and any serious adverse event (SAE).

Individuals who do not meet the criteria for participation in this trial (screen failure) for reasons such as fever due to a brief acute upper respiratory illness, having taken a prohibited over-the-counter medication within the excluded period, recent blood donation, or who could not be enrolled within the screening window for logistical reasons, may be allowed one opportunity to be rescreened at the discretion of the investigator or designee. The rescreened patient will be assigned a new patient number and all screening assessments will be repeated. Patients will not be rescreened more than once.

9.1.2 Treatment Period 1 (Visits 2 to 5 [Days 1 to 21])

This treatment period will consist of a dose-titration phase of approximately 14 days followed by a maintenance-dose phase of approximately 7 days, where the individually determined optimized dose level remains unchanged for the remainder of the treatment period after titration. On the days of scheduled MAS assessments other than Visit 1 (i.e., Visits 2 and 5), patients will attend the trial site without having administered any IMP in the morning. On the days of MAS assessment, patients who are taking baclofen and/or tizanidine as part of their optimized antispasticity therapy should take their regular morning dose of either or both medication(s) at least 1 hour before administration of IMP. Patients will continue to take their current oral MS antispasticity medications without any changes in dose.

9.1.2.1 Visit 2 (Day 1)

Patients will return to the site in the morning of Day 1 when eligibility will be confirmed and patients will be randomized.

The following assessments/procedures will be performed on Day 1 predose:

- Eligibility check
- Randomization ([Section 7.2](#))
- Concomitant medications review
- AE review
- Examination of oral mucosa
- Body weight measurement

- Vital signs measurement
- Urine drug screen (including THC)
- Urine pregnancy test (if appropriate)
- PK blood sampling for IMP ([Section 9.2.12.1](#))
- MAS assessment
- T25FW test ([Section 9.2.15.4](#))
- C-SSRS assessment
- IMP dosing training ([Section 9.2.14.3](#))
- IMP dispensing

Following predose assessments and after IMP dosing training and dispensing, site staff will observe dosing by the patient and verify that IMP was correctly administered.

Patients will administer a single dose of IMP with a standardized snack containing at least 300 kcal (of which approximately 30 kcal is composed of fat) at the trial site under the supervision of site staff.

The following assessments/procedures will be performed 2 to 4 hours postdose:

- MAS assessment (3 hours \pm 15 minutes postdose)
- AE review
- Vital signs measurement
- PK blood sampling for IMP ([Section 9.2.12.1](#))

The patient will be provided dosing instructions and advised to contact the investigational site when in doubt about changes in the daily dose of IMP. The patient will be instructed to record IMP doses administered in the patient electronic diary.

The exact time of PK blood sampling and the time of the patient's snacks and meals should be recorded.

Following Visit 2, patients will titrate their daily dose of IMP for approximately 14 days until they achieve an optimized dose with an approximately 15-minute interval between sprays; patients should divide doses greater than 1 spray/day into a morning dose and an evening dose. Administration of the morning and evening doses of IMP should be maintained around the same time each day in a consistent manner in relation to food consumption, i.e., within 30 minutes after starting a snack or meal.

Patients should be reminded to record their 11-point NRS spasticity score, spasm count, and use of antispasticity medications in the electronic diary once daily, around the same time each day, preferably in the evening before retiring to sleep. In addition, on the day

before Visits 4 and 5, patients will be prompted to record whether they started their morning and evening doses of IMP within 30 minutes of a snack or meal.

Each site will have the option to follow up with the patient through telephone calls during the titration phase to monitor the patient's titration, safety and tolerance, and electronic daily diary reporting.

9.1.2.2 Visit 3 (Day 8, Phone Call)

Visit 3 will occur 7 days after the first dose of IMP and will consist of a phone call from site staff to patients to monitor adherence with IMP administration and advise on dose titration if required. Concomitant medications and AEs will be collected during this call.

9.1.2.3 Visit 4 (Day 15) and Visit 5 (Day 21)

Visits 4 and 5 will occur 14 and 20 days after the first dose of IMP, respectively. A visit window of ± 1 and ± 2 days, respectively, from the scheduled visit date is permitted, but it is preferred that the visit is performed on the scheduled visit day, where possible.

Once a stable daily dose has been reached, patients should gradually decrease the interval between sprays to a target interval of approximately 1 minute between sprays. Patients should continue IMP administration at the same dose level achieved at the end of titration (i.e., their daily optimized dose) ± 1 spray divided into a morning dose and an evening dose for approximately 7 days (maintenance-dose phase). Administration of the morning and evening doses of IMP should be maintained around the same time of each day in a consistent manner in relation to food consumption, i.e., within 30 minutes after starting a snack or meal.

On Visit 5, patients will administer their morning dose of IMP with a standardized snack containing at least 300 kcal (of which approximately 30 kcal is composed of fat) at the trial site under the supervision of site staff. The IMP will not be administered in the evening of Visit 5 (Day 21).

The following assessments/procedures will be performed at these visits, unless otherwise indicated:

- MAS assessment (Visit 5 [3 hours ± 15 minutes after the first spray of the morning dose] only)
- T25FW test (Visit 5 only)
- Concomitant medications review
- AE review

- Physical examination (Visit 5 only)
- Examination of the oral mucosa
- Vital signs measurement
- 12-lead ECG (Visit 5 only)
- Clinical laboratory sampling (hematology and biochemistry) (Visit 5 only)
- PK blood sampling for IMP ([Section 9.2.12.1](#))
- MSSS-88 assessment (Visit 5 only)
- C-SSRS assessment
- IMP dosing at the investigational site (Visit 5 [morning] only)
- IMP dispensing (Visit 4 only)
- IMP collection and compliance review ([Section 9.2.16](#))

The exact time of PK blood sampling and the time of the patient's snacks and meals should be recorded.

Patients should be reminded to record their 11-point NRS spasticity score, spasm count, use of antispasticity medications, and IMP dosing in the electronic diary once daily, around the same time each day, preferably in the evening before retiring to sleep.

9.1.3 Washout Period (Days 22 to 30)

A washout period of at least 7 days will separate the 2 treatment periods. Following the final dose of IMP in Treatment Period 1, in the morning of Visit 5 (Day 21), patients will discontinue treatment with IMP for the 7 days prior to Visit 6 (Day 31). Patients will continue to take their current optimized oral MS antispasticity medications without any changes in dose. Patients should be reminded to record their 11-point NRS spasticity score, spasm count, and use of antispasticity medications in the electronic diary once daily, around the same time each day, preferably in the evening before retiring to sleep, for at least 7 days prior to Visit 6.

9.1.4 Treatment Period 2 (Visits 6 to 9 [Days 31 to 51])

This treatment period will consist of a dose-titration phase of approximately 14 days followed by a maintenance-dose phase of approximately 7 days, where the individually determined optimized dose level remains unchanged for the remainder of the treatment period after titration. On the days of scheduled MAS assessments other than Visit 1 (i.e., Visits 6 and 9), patients will attend the trial site without having administered any IMP in the morning. On the days of MAS assessment, patients who are taking baclofen and/or tizanidine as part of their optimized antispasticity therapy should take their regular

morning dose of either or both medication(s) at least 1 hour before administration of IMP. Patients will continue to take their current optimized oral MS antispasticity medications without any changes in dose.

9.1.4.1 Visit 6 (Day 31)

Visit 6 will occur 30 days after the first dose of IMP. A visit window of ± 1 day from the scheduled visit date is permitted, but it is preferred that the visit is performed on the scheduled visit day, where possible.

The following assessments/procedures will be performed on Day 31 predose:

- Concomitant medications review
- AE review
- Examination of oral mucosa
- Body weight measurement
- Vital signs measurement
- Urine pregnancy test (if appropriate)
- PK blood sampling for IMP ([Section 9.2.12.1](#))
- MAS assessment
- T25FW test
- C-SSRS assessment
- IMP dispensing

Following predose assessments and IMP dispensing, patients will administer a single dose of IMP with a standardized snack containing at least 300 kcal (of which approximately 30 kcal is composed of fat) at the trial site under the supervision of site staff.

The following assessments/procedures will be performed 2 to 4 hours postdose:

- MAS assessment (3 hours ± 15 minutes postdose)
- AE review
- Vital signs measurement
- PK blood sampling for IMP ([Section 9.2.12.1](#))

The patient will be provided dosing instructions and advised to contact the investigational site when in doubt about changes in the daily dose of IMP. The patient will be instructed to record IMP doses administered in the patient electronic diary.

The exact time of PK blood sampling and the time of the patient's snacks and meals should be recorded.

Following Visit 6, patients will titrate their daily dose of IMP for approximately 14 days until they achieve an optimized dose with an approximately 15-minute interval between sprays; patients should divide doses greater than 1 spray/day into a morning dose and an evening dose. Administration of the morning and evening doses of IMP should be maintained around the same time each day in a consistent manner in relation to food consumption, i.e., within 30 minutes after starting a snack or meal.

Patients should be reminded to record their 11-point NRS spasticity score, spasm count, and use of antispasticity medications in the electronic diary once daily, around the same time each day, preferably in the evening before retiring to sleep. In addition, on the day before Visits 8 and 9, patients will be prompted to record whether they started their morning and evening doses of IMP within 30 minutes of a snack or meal.

Each site will have the option to follow up with the patient through telephone calls during the titration phase to monitor the patient's titration, safety and tolerance, and electronic daily diary reporting.

9.1.4.2 Visit 7 (Day 38, Phone Call)

Visit 7 will occur 7 days after the first dose of IMP during Period 2 and will consist of a phone call from site staff to patients to monitor adherence with IMP administration and advise on dose titration if required. Concomitant medications and AEs will be collected during this call.

9.1.4.3 Visit 8 (Day 45) and Visit 9 (Day 51, End of Treatment)

Visits 8 and 9 will occur 44 and 50 days after the first dose of IMP, respectively. A visit window of ± 1 and ± 2 days, respectively, from the scheduled visit date is permitted, but it is preferred that the visit is performed on the scheduled visit day, where possible.

Once a stable daily dose has been reached, patients should gradually decrease the interval between sprays to a target interval of approximately 1 minute between sprays. Patients should continue IMP administration at the same dose level achieved at the end of titration (i.e., their daily optimized dose) ± 1 spray divided into a morning dose and an evening dose for approximately 7 days (maintenance-dose phase). Administration of the morning and evening doses of IMP should be maintained around the same time of each day in a

consistent manner in relation to food consumption, i.e., within 30 minutes after starting a snack or meal.

On Visit 9, patients will administer the morning dose of IMP with a standardized snack containing at least 300 kcal (of which approximately 30 kcal is composed of fat) at the trial site under the supervision of site staff. The IMP will not be administered in the evening of Visit 9 (Day 51).

The following assessments/procedures will be performed at these visits, unless otherwise indicated:

- MAS assessment (Visit 9 [3 hours ± 15 minutes after the first spray of the morning dose] only)
- T25FW test (Visit 9 only)
- Concomitant medication review
- AE review
- Physical examination (Visit 9 only)
- Examination of the oral mucosa
- Vital signs measurement
- 12-lead ECG (Visit 9 only)
- Clinical laboratory sampling (hematology and biochemistry) (Visit 9 only)
- PK blood sampling for IMP ([Section 9.2.12.1](#))
- MSSS-88 assessment (Visit 9 only)
- C-SSRS assessment
- IMP dosing at the investigational site (Visit 9 [morning] only)
- IMP dispensing (Visit 8 only)
- IMP collection and compliance review

The exact time of PK blood sampling and the time of the patient's snacks and meals should be recorded.

Patients should be reminded to record their 11-point NRS spasticity score, spasm count, use of antispasticity medications, and IMP dosing in the electronic diary once daily, around the same time each day, preferably in the evening before retiring to sleep.

If the decision is made to discontinue IMP early, the patient concerned will be encouraged to remain in the study for the duration of the treatment period in which they discontinue IMP and will complete an End of Treatment Visit (Visit 9) at the end of that period.

9.1.5 Safety Follow-up Visit (Visit 10 [Day 58])

The Safety Follow-up Visit will occur 7 days after the last dose of IMP or after the End of Treatment visit (Visit 9), whichever is later. A visit window of +3 days from the scheduled visit date is permitted, but it is preferred that the visit is performed on the scheduled visit day, where possible.

The following assessments/procedures will be performed:

- Concomitant medication review
- AE review
- Examination of oral mucosa
- Body weight measurement
- Vital signs measurement
- Dipstick urinalysis
- Serum pregnancy test (if appropriate)
- C-SSRS assessment

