--	---

	
patients who are taking baclofen and/or tizanidine as part of their optimized antispasticity therapy should take their regular morning dose of either or both medication(s) at least 1 hour before the administration of IMP. Administration of the morning dose of IMP with a standardized snack containing at least 300 kcal (of which approximately 30 kcal is composed of fat) will occur at the trial site under the supervision of site staff; MAS assessments will occur at scheduled time points before (Visits 2 and 6 [predose]) and after (Visits 2, 5, 6, and 9 [3 hours ± 15 minutes postdose]) IMP administration.
 
A washout period of at least 7 days will separate the 2 treatment periods. During the washout period, patients will continue to take their current MS antispasticity medications without any changes in dose.
 
Patients who complete the 2 treatment periods will complete an End of Treatment Visit (Visit 9). Patients who discontinue IMP early will be encouraged to remain in the study for the duration of the treatment period in which they discontinue IMP and will complete an End of Treatment Visit (Visit 9) at the end of that period. A Safety Follow-up Visit (Visit 10) will occur 7 (+3) days after the last dose of IMP or after the End-of-Treatment visit (Visit 9), whichever is later, for all patients.

Primary Endpoint	
Change in Lower Limb Muscle Tone-6 (LLMT-6; defined as the average of the 6 individual MAS transformed scores of knee flexors, knee extensors, and plantar flexors on both sides of the body) from Day 1 predose to Day 21 and from Day 31 predose to Day 51
 
The MAS scores are transformed using the following algorithm: MAS untransformed [to MAS transformed] scores; 0[0], 1[1], 1+[2], 2[3], 3[4], and 4[5].

Secondary Endpoints	
Efficacy:
 
• Change in Lower Limb Muscle Tone-4 (LLMT-4; defined as the average of the 4 individual MAS transformed scores of knee flexors and knee extensors on both sides of the body) from Day 1 predose to Day 21 and from Day 31 predose to Day 51 
Safety:
 
• Frequency of treatment-emergent adverse events (TEAEs)• Change from baseline to each assessment timepoint by treatment period for the following:
• Clinical laboratory parameters

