Patients who complete the 2 treatment periods will complete an End of Treatment Visit (Visit 9). Patients who discontinue IMP early will be encouraged to remain in the study for the duration of the treatment period in which they discontinue IMP and will complete an End of Treatment Visit (Visit 9) at the end of that period. A Safety Follow-up Visit (Visit 10) will occur 7 (+3) days after the last dose of IMP or after the End of Treatment visit (Visit 9), whichever is later, for all patients.

A schematic ([Figure 1-1](#)), presented at the end of [Section 1](#), depicts the overall trial design. More detailed information on treatment and trial procedures is provided in [Section 8](#) and [Section 9](#), respectively.

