Should a patient request or decide to withdraw from the trial, all efforts must be made to complete and report the observations as thoroughly as possible up to the date of withdrawal. Patients withdrawing due to an AE should be followed up according to [Section 12.7](#). All information should be reported on the applicable eCRF pages (refer to [Section 9.2](#)). A Safety Follow-up Visit should take place 7 (+3) days after last dose of IMP or after the End of Treatment visit (Visit 9), whichever is later (refer to [Section 9.1.5](#)). If withdrawing patients decline to give a reason for withdrawal of consent, the investigator must respect the patients' wishes.

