10.1.3 Target Days and Visit Window

Visit windows are summarized in [Table 10.1-3](#) for efficacy data and urine drug screen collection and, in [Table 10.1-2](#) for all other safety endpoints.

When there are multiple observations within a visit window, the value closest to the target day will be analyzed (as described in [Table 10.1-1](#)).

For safety assessments, on-treatment assessments will be preferred to off-treatment ones.

In case of ties between observations located on different sides of the target, the observation with the earliest date/time will be used. In case of ties between observations located on the same side of the target, (i.e., more than one value for the same day but at different time), the observation with the earliest date/time will be used. However, in case of non-respect of wash-out period, the one done at least 7 days after last Period 1 dosing date will be preferred.

For efficacy, PRO endpoints visit windowing will apply whether patient is on or off treatment.

Table 10.1-1 Longitudinal Assessment – Analysis Day and Target Day

Treatment Period	Visit / Day	Analysis visit	Target Day (defined by period)	Observation used for analysis, if more than one exists
Screening	Visit 1 / Day -28 to -1	Screening	Day -28 to -1	Latest value
Period 1	Visit 2 / Day 1	Day 1	Day 1*	Closest to Target Day But Day 1 H0 should be before 1 st IMP intake and D1H3 should be post IMP intake
	Visit 3 / Day 8	Day 8	Day 8	Closest to Target Day
	Visit 4 / Day 15	Day 15	Day 15	Closest to Target Day
	Visit 5 / D21	D21	D21	Closest to Target Day
Period 2	Visit 6 / Day 31	Day 1	Day 1*	Closest to Target Day But Day 1 H0 should be before 1 st IMP intake and

Treatment Period	Visit / Day	Analysis visit	Target Day (defined by period)	Observation used for analysis, if more than one exists
				D1H3 should be post IMP intake.
	Visit 7 / Day 38	Day 8	Day 8	Closest to Target Day
	Visit 8 / Day 45	Day 15	Day 15	Closest to Target Day
	Visit 9 / Day 51	D21	D21	Closest to Target Day
Follow-up	Visit 10 / Day 58	Day 28	Day 28**	Closest to Target Day

H = Hours; IMP = Investigational medical product.

** Day 1 is based on the date of IRT call within each period*

*** Day 28 relative to the period where IMP is permanently discontinued thus visit is expected between Day 25 and Day 31*

Table 10.1-2 Longitudinal Assessment – Target Day and Visit Window – Part 1

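### The protocol text allows no early Safety Follow-up Visit, but the schedule of assessments and a SAP footnote allow it up to 3 days early

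*Protocol*

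**What the plan says.** The protocol text gives one rule in four places. Section 9.1.5 counts 7 days from the later of the last dose and Visit 9, and then sets the tolerance: "A visit window of +3 days from the scheduled visit date is permitted". The synopsis and Section 4.1 say the visit "will occur 7 (+3) days after the last dose of IMP or after the End of Treatment visit". Section 10 repeats it for withdrawals: "A Safety Follow-up Visit should take place 7 (+3) days after last dose of IMP". None of the four allows an earlier visit.

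The schedule of assessments in protocol Appendix 1 shows the follow-up column as Day 58 with a window of 3 days on either side.

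The SAP, in Table 10.1-1 (Section 10.1.3), sets the target at Day 28 of the period in which treatment is permanently stopped, and the footnote adds: "thus visit is expected between Day 25 and Day 31".

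Visit 9 has its own tolerance. Section 9.1.4.3 says of Visits 8 and 9: "A visit window of ± 1 and ± 2 days, respectively, from the scheduled visit date is permitted". For a patient who completes treatment, the last dose is taken on the morning of Visit 9, because no evening dose is given that day.

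**The concern.** A window that runs only later and a window that runs both ways cannot both hold. A site that books from the schedule can see a patient earlier than the text permits, and the SAP footnote would treat that visit as expected.

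For a patient who completes dosing, Visit 10 is the only scheduled safety contact after the day of the final dose. It closes routine adverse event collection (protocol Section 12.6). It also provides the last serum pregnancy test and the follow-up C-SSRS that SAP Section 12.7.5.3 uses for its withdrawal assessment. An early visit shortens the observation behind all of these.

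There is also a labelling problem. SAP Section 10.1.1 extends the on-treatment safety period by 4 days for the C-SSRS and starts follow-up only after that. SAP Section 12.7.5.3 calls any C-SSRS after the last intake follow-up. At the text's timing the two rules agree on Visit 10. At the schedule's earliest timing they may not.

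**Working it through.** **Inputs.** Visit 9: Day 51 ± 2, so Day 49 to 53 (protocol 9.1.4.3). Last dose of a completer: the morning of Visit 9. Visit 10 in the text: 7 to 10 days after the later of last dose and Visit 9 (protocol synopsis, 4.1, 9.1.5, 10). Visit 10 in the schedule: Day 58 ± 3 (protocol Appendix 1). Visit 10 in the SAP: Day 25 to 31 of the period (Table 10.1-1 footnote).

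**The plan's own figure.** Nominal Visit 10 = 51 + 7 = Day 58, as stated.

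**Is the SAP window a third rule?** With Period 2 starting on Day 31, period day = trial day - 31 + 1. Day 58 becomes 58 - 31 + 1 = 28, the SAP target. SAP Day 25 is trial Day 31 + 24 = 55, and SAP Day 31 is 31 + 30 = 61. The schedule gives 58 - 3 = 55 to 58 + 3 = 61. The SAP footnote is the schedule's window on the period clock, so there are two rules. (If Visit 6 falls on Day 30 or 32, the SAP range shifts by one day.)

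**Gap from last dose to Visit 10.** Gap = Visit 10 day - Visit 9 day, with the schedule's Day 58 first read as a fixed trial day:

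| Visit 9 (last dose) | Text allows Visit 10 on | Gap, text | Schedule allows | Gap, schedule |
|---|---|---|---|---|
| Day 49 | 56 to 59 | 7 to 10 | 55 to 61 | 6 to 12 |
| Day 50 | 57 to 60 | 7 to 10 | 55 to 61 | 5 to 11 |
| Day 51 | 58 to 61 | 7 to 10 | 55 to 61 | 4 to 10 |
| Day 52 | 59 to 62 | 7 to 10 | 55 to 61 | 3 to 9 |
| Day 53 | 60 to 63 | 7 to 10 | 55 to 61 | 2 to 8 |

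If the 3 days either side are instead centred on 7 days after the last dose, the gap is 7 - 3 = 4 to 7 + 3 = 10 days whatever the day of Visit 9. The minimum of 4 days therefore holds under both readings when Visit 9 is on time.

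The windows also differ at the late end on the fixed-day reading. After a Day 53 Visit 9, only Days 60 and 61 satisfy both rules.

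**C-SSRS label.** This takes the end-of-treatment date to be the last-dose date. The on-treatment window in SAP Section 10.1.1 then runs to last dose + 4. For a last dose on Day 51 that is Day 55, so a Visit 10 on Day 55 lies inside it, while SAP Section 12.7.5.3 calls the same assessment follow-up. At the text's minimum, 7 > 4, so the overlap cannot occur.

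**Adverse events.** The on-treatment tail is 14 days (SAP 10.1.1), so an event recorded by any of these visits keeps the same class. What changes is how much of the tail is routinely observed: at least 7 of 14 days under the text, and as little as 4 of 14 under the schedule with an on-time Visit 9.

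**The case against.** The strongest reply is that four concordant statements in the text outweigh one table cell, that Section 9.1.5 prefers the scheduled day, and that the SAP footnote is an analysis expectation and not an instruction to sites. The SAP's data rules are also looser than its footnote: Table 10.1-2 takes the follow-up C-SSRS and oral mucosa examination from any time after the last dose. All of this is fair and limits the practical effect, but a site following the schedule still has written cover for an early visit.

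Three stronger readings are tempting, and the documents do not support them.

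- A reader might count three competing windows. The arithmetic shows two.
- A reader might take 2 days as the finding. That needs Visit 9 at its latest (Day 53), Visit 10 at its earliest (Day 55), and Day 58 read as a fixed trial day. The SAP's copy of the schedule heads the column with an alternative of 7 days after the final dose or the end-of-treatment visit, which points to a dose-relative reading. The matching heading is not legible in the machine-read protocol table, so the fixed-day reading cannot be relied on.
- A reader might infer that Visit 10 is the only off-drug safety contact. It is not. Visit 6 before dosing follows a washout of at least 7 days and includes adverse event review, vital signs, oral mucosa examination, a pregnancy test and C-SSRS.

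Safeguards beyond Visit 10 also exist. Deaths and new related serious events that the investigator learns of within 28 days of the final dose are reported (protocol 12.3). Related events are followed to resolution or stability (12.7). Pregnancies within 3 months of the last dose are reported (12.4). These stand, but the 28-day rule does not require active monitoring.

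The plus-or-minus sign comes from a damaged table, so a reading error is conceivable. The SAP's symmetric Day 25 to 31 supports it independently.

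**Conclusion.** The inconsistency is real and minor. The text sets a minimum of 7 days from the later of last dose and Visit 9. The schedule and the SAP footnote allow 4 days with Visit 9 on Day 51, a loss of up to 3 of 7 days. The smaller gap of 2 days belongs to the corner case described above and should not be quoted as typical. The documents give no basis for estimating how often early visits occur.

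The effect is on safety follow-up: the length of routine adverse event collection after the final dose, and the label of a C-SSRS taken 4 days or less after it. No efficacy estimate, type I error or power figure is touched. The conclusion assumes that a completer's last dose is on the day of Visit 9 and that the schedule's sign has been read correctly. It does not say which window is right.

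**What to change.** Reconcile protocol Appendix 1, the synopsis, Sections 4.1, 9.1.5 and 10, and the SAP Table 10.1-1 footnote to one window with one stated anchor (last dose or Visit 9, or a trial day). Check the SAP's copy of the schedule in the same edit, and make SAP Sections 10.1.1 and 12.7.5.3 agree on how a C-SSRS in the first 4 days after the last dose is labelled.

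Derive the days from last dose to Visit 10 and list them for each patient alongside the adverse event and C-SSRS follow-up summaries. The SAP reports a sample size re-estimation already done, so the trial is under way. A wording change helps only the visits still to come, while the listing covers every patient.

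The cost is one table cell, a footnote, a sentence in the SAP and one derived variable. No new data are needed.
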